1.4.3 Handling of missing values/censoring/discontinuations

The derivation of the primary efficacy variable from the sequence of overall lesion responses recorded at each assessment followed the Novartis guidance ‘Guidelines for Response, Duration of Overall Response, TTF, TTP, Progression-Free Survival and Overall Survival (based on RECIST)’. Subjects not qualifying for confirmed CR or PR and without SD after more than 6 weeks or early progression within the first 12 weeks were classified as ‘UNK’ for their best overall response.

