7.4 Efficacy

Tumor evaluation

Disease status will be based on CT/MRI scans and/or chest x-ray performed maximum ca. 2 weeks before baseline, thereafter after week 8, 16, 28, 40, 52 and X, respectively at final visit. If medically indicated, unscheduled CT/MRI examinations and/or chest x-ray will be performed at the investigator's discretion. Response status will be evaluated using RECIST criteria (please see Post-text supplement 1). The evaluation of the central radiologist will be used.

At baseline and 1st comparative FDG-PET assessment at visit 5 can be carried out optional in non-German-centers in order to provide this additional perspective on changes in tumor activity induced by the therapy and give data on correlation of PET as an indicator for progression or response. Although ¹⁸F-FDG-PET functional imaging may be valuable as a complement to standard anatomical imaging (CT or MRI) in any tumor assessment (identification of new lesions or of newly active foci in otherwise inactive lesions), the primary variable for efficacy assessment will be that obtained by standard anatomical imaging.

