1.4 Analysis of the primary objective(s)

1.4.1 Variable

The primary variable is defined as the proportion of patients in whom a best overall response of complete (CR) or partial (PR) response or stable disease (SD) was observed at 16 weeks according to RECIST (version 1.0, [Therasse et al. 2000](#)) based on local radiologic assessments.

The best overall response for each patient was determined from the sequence of overall (lesion) responses at Visit 4/Week 8 and Visit 6/Week 16, respectively, according to the following rules (see Post-text supplement 1 to the study protocol):

- CR = at least two determinations of CR at least 4 weeks apart before progression.
- PR = at least two determinations of PR or better at least 4 weeks apart before progression (and not qualifying for a CR).
- SD = at least one SD assessment > 6 weeks after start of treatment (and not qualifying for CR or PR).
- PD = progression or death due to underlying cancer ≤ 16 weeks after start of treatment (and not qualifying for CR, PR or SD). Patients with symptoms of rapidly progressing disease without radiologic evidence will be classified as progression only when clear evidence of clinical deterioration is available and patient discontinued due to 'Disease progression'. Furthermore, patients without radiologic evidence for progression who were prematurely discontinuing from the study for 'unsatisfactory therapeutic effect', 'new cancer therapy' or 'death' (from any reason) will be classified as progression.
- UNK = all other cases (i.e. not qualifying for confirmed CR or PR and without SD after more than 6 weeks or early progression within the first 16 weeks)

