1.4.2 Statistical hypothesis, model, and method of analysis

The best overall response rate (CR/PR/SD/PD/UNK) was presented together with the appropriate two-sided confidence interval for the ITT set. Since the one-sided alpha was set to 10%, two-sided 80% confidence intervals were presented. Exact confidence intervals were computed according to the method of Clopper and Pearson.

The absolute number of patients showing a best overall response of CR, PR or SD was determined to conclude preliminary activity or non-activity of the study drugs in this patient population according to the rules outlined in CSP [section 10.2](#). Furthermore, the lower limit of the confidence interval was used to support the decision in favor of p_0 or p_1 : if the lower limit of the confidence interval overlapped p_0 , the hypothesis that p is greater than or equal to p_1 could be rejected; on the other side, if the lower limit of the confidence interval excluded p_0 , the hypothesis that p is greater than or equal to p_1 could be accepted.

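### SAP 1.4.3 uses a 12-week limit for early progression where SAP 1.4.1 and the protocol use 16 weeks, so a narrow group of patients is PD under one section and UNK under the other

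*SAP*

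**What the plan says.** SAP 1.4.1 defines best overall response and carries a 16-week limit twice. The progression rule reads "PD = progression or death due to underlying cancer ≤ 16 weeks after start of treatment", and the unknown category is the remainder, meaning no confirmed response and "without SD after more than 6 weeks or early progression within the first 16 weeks". The section refers to post-text supplement 1 of the protocol, whose PD and UNK rules also use 16 weeks.

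SAP 1.4.3, on missing values and discontinuations, restates the unknown rule in nearly the same terms, but there patients lacking a confirmed response and "without SD after more than 6 weeks or early progression within the first 12 weeks were classified as" UNK.

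Three other provisions decide who is affected:

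- SD requires "at least one SD assessment > 6 weeks after start of treatment (and not qualifying for CR or PR"), so a single SD at week 8 settles the category.
- Best overall response is built from the "overall (lesion) responses at Visit 4/Week 8 and Visit 6/Week 16, respectively".
- Protocol 7.4 schedules scans before baseline and "thereafter after week 8, 16, 28, 40, 52 and X". None is scheduled at week 12.

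SAP 1.4.2 makes the split between PD and UNK visible: "The best overall response rate (CR/PR/SD/PD/UNK) was presented together with the appropriate two-sided confidence interval for the ITT set". SAP 1.4.4 repeats the five categories for the PP set.

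**The concern.** Both sections describe the derivation of the same variable, so a programmer cannot follow both for a patient whose first progression falls after week 12 and by week 16. The SAP does list its departures from the protocol (local instead of central tumor assessment, ITT instead of PP for the primary analysis). A shorter progression limit is not among them, so 1.4.3 does not read as a deliberate change.

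At stake is how the failures are described. The split between PD and UNK tells the reader how many failures were observed progression and how many had no usable outcome. Applying the 12-week sentence would report some documented progressors as unknown.

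**Working it through.** **1. The plan's own design figures.** Inputs from SAP 1.6: p0 = 20%, p1 = 40%, 11 or more responders of 36 (arm I), 8 or more of 24 (arms II and III). With X binomial:

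- n = 36: P(X ≥ 11 | 0.20) = 0.0889; P(X ≤ 10 | 0.40) = 0.0904. Stated: 8.9% and 9.0%.
- n = 24: P(X ≥ 8 | 0.20) = 0.0892; P(X ≤ 7 | 0.40) = 0.1919. Stated: 8.9% and 19.2%.

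The figures reproduce. They count CR, PR and SD only, so they do not depend on how non-responders are divided between PD and UNK.

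**2. The limits side by side.**

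| Place | Rule | Limit |
|---|---|---|
| Protocol supplement 1 | PD and UNK | 16 weeks |
| SAP 1.4.1 | PD | 16 weeks |
| SAP 1.4.1 | UNK | 16 weeks |
| SAP 1.4.3 | UNK | 12 weeks |

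**3. Which scan sequences change category.** Each of the two assessments can be CR, PR, SD, PD or UNK, giving 5 × 5 = 25 combinations. The best-overall-response rules were applied to all 25 at nominal scan times, once with a 16-week and once with a 12-week limit. Three differ:

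| Week 8 | Week 16 | 16-week limit | 12-week limit |
|---|---|---|---|
| UNK or not assessed | PD | PD | UNK |
| PR, unconfirmed | PD | PD | UNK |
| CR, unconfirmed | PD | PD | UNK |

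SD then PD is SD under both limits. PD at week 8 is PD under both. No combination enters or leaves CR, PR or SD.

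Patients who progress clinically or die of their cancer after week 12 and by week 16, without earlier SD or confirmed response, are also affected. So are the discontinuations that 1.4.1 counts as progression, if they fall in that interval. The ITT definition in SAP 1.1 has no week limit, so the denominator stays the same.

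**4. Size per patient.** One patient is 1/36 = 2.8 percentage points in arm I and 1/24 = 4.2 points at the planned size of arms II and III. Protocol section 10 reports 8 patients enrolled in arm III; if all 8 are in the ITT set, one patient is 1/8 = 12.5 points.

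**5. Illustration.** Assume 18 of 36 patients in arm I are PD and none UNK under the 16-week limit. Neither number is in the documents. Let k patients be affected, and use the SAP's two-sided 80% Clopper-Pearson intervals:

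| k | PD | UNK |
|---|---|---|
| 0 | 18/36 = 50.0% (38.2 to 61.8) | 0/36 = 0% (0 to 6.2) |
| 1 | 17/36 = 47.2% (35.5 to 59.1) | 1/36 = 2.8% (0.3 to 10.4) |
| 3 | 15/36 = 41.7% (30.4 to 53.7) | 3/36 = 8.3% (3.1 to 17.6) |

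**The case against.** The strongest reply is that 12 is a leftover. The section that defines the variable says 16 in both rules, the protocol supplement agrees, and a 12-week limit fits poorly with a schedule whose second scan is at week 16. If 1.4.1 was programmed, nothing moves. That is a plausible inference and it stands as such, but the SAP does not say which sentence prevailed.

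The second reply is that the effect is small. The decision rests on the CR+PR+SD count, and the protocol places the category-by-category table under supportive analyses (10.4.4). PFS and TTP use the date of documented progression, so these patients are not lost there. All of this stands and limits the point to the PD and UNK rows.

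A reader might also infer three stronger things:

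- **That every progression seen by scan after week 8 is in dispute.** It is not. A patient with SD at week 8 is SD whatever week 16 shows.
- **That the PD rate is understated.** That follows only if the 12-week sentence was applied.
- **That a week 16 PD scan done a few days late becomes UNK because no visit tolerance is stated.** This is one possible reading. SAP 1.4.1 ties the derivation to the named Visit 4 and Visit 6 assessments, so a slightly late Visit 6 scan can still count as Visit 6. SAP 1.4.3 also says that the derivation followed a sponsor guideline, which is not among the documents and may deal with timing.

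**Conclusion.** The inconsistency is real but minor. One number in SAP 1.4.3 disagrees with SAP 1.4.1 and with the protocol supplement that 1.4.1 cites. It affects only patients with neither a qualifying SD nor a confirmed response whose first progression, or death counted as progression, falls after week 12 and by week 16.

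If the 12-week sentence is applied, each such patient moves from PD to UNK in the ITT and PP category tables, by 2.8 points at n = 36 or 4.2 points at n = 24. These sizes use the planned evaluable numbers, because the ITT numbers are not given. The number of affected patients is unknown. SAP 1.5.1 notes that no patient reached a best overall response of CR or PR, but this does not exclude an unconfirmed response at week 8.

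The proportion with CR, PR or SD, its denominator, the error rates and the activity decision are the same under either limit.

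**What to change.** In SAP 1.4.3, change the limit for early progression from 12 to 16 weeks, so that it matches SAP 1.4.1 and protocol post-text supplement 1. Because the SAP describes the analysis in the past tense, add a sentence stating which limit was programmed. If it was 12 weeks, re-run the PD and UNK rows of the ITT and PP tables.

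If the sponsor prefers to tie the limit to the Week 16/Visit 6 assessment rather than to a number of weeks, the same wording must go into the PD clause of 1.4.1, the UNK clause of 1.4.1 and 1.4.3. Changing the PD clause alone would create a new mismatch: a Visit 6 progression after day 112 (16 × 7), without earlier SD or confirmed response, would be PD by one clause and UNK by the others.

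The basic correction costs one number and one sentence. Sample size, decision rule and data collection are untouched.

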1.4.4 Supportive analyses

The number and percentage of patients showing a best overall response of CR, PR or SD as well as the number and percentage of patients for each category (CR/PR/SD/PD/UNK) was additionally presented for the per-protocol (PP) set.

Additionally, for patients who entered the follow-up period starting after Visit 6/Week 16, the best overall response was determined using all available local tumor assessments.

1.5 Analysis of secondary objectives

1.5.1 Efficacy (secondary)

Secondary efficacy variables were analyzed for the ITT set.

Objective response rate (ORR) was defined as the proportion of patients in whom a complete (CR) or partial (PR) response was observed at Visit 6/Week 16 according to RECIST (version 1.0) based on central radiologic review. Absolute and relative frequencies were presented together with the appropriate exact confidence interval.

Duration of stable disease (CR, PR or SD) applied only to those patients whose best overall response was CR, PR or SD based on local radiologic assessments and was defined as the time from start of treatment to progression or death from underlying disease. Patients not experiencing progression or death at 16 weeks were censored with the date of their last tumor assessment. Duration of response was explored using the Kaplan-Meier method. The Kaplan-Meier estimate for median duration of response as well as the Kaplan-Meier curve was displayed. Although duration of response (CR or PR) was planned to be analyzed within the protocol, this was changed to reach a more valuable analysis since no patient reached a best overall response of CR or PR.

Progression-free survival (PFS) was defined as the time from the date of start of treatment to the date of event defined as the first documented progression or death from any cause. If a patient had not had an event, PFS was censored at the date of the last adequate tumor assessment, which was the date of Visit 6 for the core study phase and the last available tumor assessment for the follow-up phase. PFS was explored by using the Kaplan-Meier method. The Kaplan-Meier estimate for median PFS as well as the Kaplan-Meier curve was displayed.

Time to progression (TTP) was defined as the time from the date of start of treatment to the date of event defined as the first documented progression or death from underlying disease. If a patient had not had an event, TTP was censored at the date of the last adequate tumor assessment, which was the date of Visit 6 for the core phase and the last available tumor

assessment for the follow-up phase. TTP was explored by using the Kaplan-Meier method. The Kaplan-Meier estimate for median TTP as well as the Kaplan-Meier curve was displayed.

Overall survival (OS) was defined as the time from the date of start of treatment to death from any cause. If a patient was not known to have died, OS was censored at the date of the last contact, which was the date of Visit 6 for the core phase and the last available visit for the follow-up phase. OS was explored by using the Kaplan-Meier method. The Kaplan-Meier estimate for median OS as well as the Kaplan-Meier curve was displayed.

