The best overall response is the best response recorded from the start of the treatment until disease progression/recurrence (taking as reference for PD the smallest measurements recorded since the treatment started). In general, the patient's best response assignment will depend on the achievement of both measurement and confirmation criteria.

To be assigned a status of PR or CR, changes in tumor measurements must be confirmed by repeat assessments that should be performed not less than 4 weeks after the criteria for response are first met.

The best overall response for each patient is determined from the sequence of overall (lesion) responses according to the following rules:

- CR = at least two determinations of CR at least 4 weeks apart before progression.
- PR = at least two determinations of PR or better at least 4 weeks apart before progression (and not qualifying for a CR).
- SD = at least one SD assessment > 6 weeks after start of treatment (and not qualifying for CR or PR).
- PD = progression or death due to underlying cancer ≤ 16 weeks after start of treatment (and not qualifying for CR, PR or SD). Patients with symptoms of rapidly progressing disease without radiologic evidence will be classified as progression only when clear evidence of clinical deterioration is available and patient discontinued due to ‘Disease progression’.
- UNK = all other cases (i.e. not qualifying for confirmed CR or PR and without SD after more than 6 weeks or early progression within the first 16 weeks)

Overall lesion responses of CR must stay the same until progression sets in, with the exception of a UNK status. A patient who had a CR can not subsequently have a lower status, e.g. PR or SD, as this would imply that one or more lesions reappeared, in which case the status would become a PD.

Overall lesion responses of PR must stay the same or improve over time until progression sets in, with the exception of a UNK status. However, if a patient has a PR ($\geq 30\%$ reduction of tumor burden compared to baseline) at one assessment, followed by a $< 30\%$ reduction from baseline at the next assessment (but not $> 20\%$ increase from previous smallest sum), the objective status at that assessment should be SD. Once a confirmed PR was seen, the overall lesion response should be considered PR (or UNK) until progression is documented.

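### SAP 1.5.1 does not say that an objective response must be confirmed, and names a different reader from the rest of the analysis, so ORR can disagree with the CR+PR rate by best overall response

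*SAP*

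**What the plan says.** SAP 1.5.1 gives ORR as the "proportion of patients in whom a complete (CR) or partial (PR) response was observed at Visit 6/Week 16 according to RECIST". The sentence goes on to name the criteria version and the reader: "according to RECIST (version 1.0) based on central radiologic review". It mentions neither best overall response nor confirmation.

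The primary variable in SAP 1.4.1 is built differently. It is a best overall response on local assessments, "determined from the sequence of overall (lesion) responses at Visit 4/Week 8 and Visit 6/Week 16, respectively", under rules such as "PR = at least two determinations of PR or better at least 4 weeks apart before progression". Protocol Post-text supplement 1, under Best overall response, has the same requirement: "To be assigned a status of PR or CR, changes in tumor measurements must be confirmed by repeat assessments", at least 4 weeks after the criteria are first met.

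Two further statements bear on this. The first change listed in SAP section 1 says that central review was incomplete and that the trial is analysed on local assessments only. SAP 1.5.1 also explains that the duration-of-response analysis was replaced "since no patient reached a best overall response of CR or PR".

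The protocol's own ORR wording does not mention confirmation either. Section 3 sets ORR at 16 weeks, and section 10.5.1 sets it at week 12.

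**The concern.** One report would carry two response rates that look like the same quantity but rest on different rules. Best overall response accepts a CR or PR only when it is seen twice. ORR, as worded, accepts the status at one visit. Because the core study has only two scheduled post-baseline scans, a response first seen at week 16 cannot be confirmed inside the window.

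ORR is a named secondary objective in a trial with no control arm. A single-scan response can reflect measurement variation, and counting it can only push ORR up. The reader adds a second difference: ORR is specified on central review, which the SAP itself says cannot support the efficacy variables. A report could therefore show a positive ORR beside a CR+PR rate of zero, with nothing in the plan to tell the reader why.

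**Working it through.** **The plan's own figures.** These are exact binomial tails for the designs in protocol 10.6 and SAP 1.6, with p0 = 20% and p1 = 40%.
- Arm I: P(X ≥ 11 | 36, 0.20) = 0.0889 and P(X ≤ 10 | 36, 0.40) = 0.0904, against 8.9% and 9.0% stated.
- Arms II and III: P(X ≥ 8 | 24, 0.20) = 0.0892 and P(X ≤ 7 | 24, 0.40) = 0.1919, against 8.9% and 19.2% stated.

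The design reproduces. These figures concern the primary variable, and nothing below depends on them.

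**Which reading of ORR is natural.** Supplement 1 defines two things: an overall lesion response at each assessment (Table Appendix 3), which needs no confirmation, and a best overall response, which does. Protocol 10.4.1 worded the primary variable as CR, PR or SD seen at 16 weeks. SAP 1.4.1 rewrote it as a best overall response but made no such change to ORR. The next paragraph of SAP 1.5.1 uses the term best overall response explicitly. The visit-level status is therefore the more natural reading of ORR, though not the only one.

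**Sequences at weeks 8 and 16.** This takes one reader, scheduled scans only, and the rules of SAP 1.4.1. Progression at week 8 ends the sequence, and CR followed by PR or SD is excluded by supplement 1.

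| Week 8 | Week 16 | ORR taken literally | Best overall response |
|---|---|---|---|
| CR or PR | CR or PR | yes | CR or PR |
| SD | CR or PR | yes | SD |
| UNK | CR or PR | yes | UNK |
| PR | SD | no | SD |
| CR or PR | PD | no | PD |
| CR or PR | UNK | no | UNK |
| SD | SD, PD or UNK | no | SD |
| UNK | SD / PD / UNK | no | SD / PD / UNK |

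Only rows two and three disagree, and in both ORR is the larger. No sequence goes the other way, because with two scans a confirmed response must still be present at week 16. The next scheduled scan is week 28 (protocol 7.4: "thereafter after week 8, 16, 28, 40, 52 and X"), which lies outside the window of SAP 1.4.1.

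**Size per patient.** Each such patient adds 1/n: 1/36 = 2.8 points, 1/24 = 4.2 points, or 1/8 = 12.5 points for the 8 patients enrolled in arm III (protocol section 10). The Clopper–Pearson limits are the α/2 quantile of Beta(x, n−x+1) and the 1−α/2 quantile of Beta(x+1, n−x). The lower limit is 0 when x = 0.

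| Arm (n) | x | Rate | 80% interval | 95% interval |
|---|---|---|---|---|
| I (36) | 0 | 0% | 0–6.2% | 0–9.7% |
| I (36) | 1 | 2.8% | 0.3–10.4% | 0.1–14.5% |
| II (24) | 0 | 0% | 0–9.1% | 0–14.2% |
| II (24) | 1 | 4.2% | 0.4–15.3% | 0.1–21.1% |

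Both levels are shown because SAP 1.5.1 gives none for ORR, SAP 1.4.2 uses 80% for the primary variable, and protocol 10.5.1 specifies 95% for ORR.

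**Effect of the reader.** A patient with PR at both visits centrally but SD locally is an ORR responder and is absent from the local CR+PR count. The reverse pattern lowers ORR. The reader can therefore separate the two rates in either direction, whatever the confirmation rule.

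**The case against.** The SAP is silent; it does not say that responses count whether or not they are confirmed. A reader might infer that it does, but the sentence cites RECIST version 1.0, and supplement 1 makes confirmation a condition for assigning PR or CR status. On that view confirmation is already included. This stands as far as it goes: the text admits two readings, and no breach is shown. Two defensible readings that give different rates still need resolving.

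A reader might also infer that any non-zero ORR would consist entirely of responses that the SAP's own rules reject, since no patient had a best overall response of CR or PR. The documents do not support that. Best overall response is read locally and ORR centrally, so a centrally confirmed PR could exist beside a local zero.

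The wording follows the protocol, and a landmark rate may legitimately differ from a best-response rate if it is labelled as such. That is fair, but the SAP supplies no such label. Finally, the consequence is small: ORR has no test or decision rule, and a patient with SD then PR is still a success in the primary CR/PR/SD count. All of that stands and limits the severity.

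**Conclusion.** The point holds as an underspecified definition of minor severity. SAP 1.5.1 leaves open whether ORR needs confirmation, and its reader conflicts with the local-only rule in SAP section 1. On the literal reading with one reader, ORR is never below the confirmed CR+PR rate, and exceeds it whenever a first response appears at week 16.

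The illustrated shift of 2.8 points in arm I or 4.2 points in arm II assumes one such patient, the planned arm size as the ITT denominator, and a confirmed count of zero in that arm. The documents do not give the number of unconfirmed week-16 responses, which may be none, and the SAP does not tie its statement of zero CR or PR to a particular arm.

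The decision rules of 11/36 and 8/24 are unaffected, because they use the primary variable of SAP 1.4.1, which is not in question here.

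**What to change.** Replace the ORR sentence in SAP 1.5.1 so that ORR is the proportion of the ITT set with a best overall response of CR or PR under SAP 1.4.1, using the week 8 and week 16 local assessments, and state the confidence level. List responses first seen at week 16 separately as unconfirmed. Report any that a later scan confirms only in the existing supportive analysis of all available local assessments (SAP 1.4.4), so that the week-16 rate keeps a single window.

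The cost is about one sentence and a listing, because the derivation already exists for the primary variable. There are two downsides. With the same reader, ORR can only stay the same or fall, and genuine responses that first appear at week 16 do not count at that time point. Moving from central to local reading could also change ORR in either direction, but it brings ORR into line with the SAP's own statement on which assessments are analysed.

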For simplification, populations for analysis, and the analysis of patient demographics/other baseline characteristics, treatment, primary and secondary efficacy variables, and safety were described without referring to a specific arm. As mentioned above, the methods of analysis were applied to each arm separately.

Changes from the analysis pre-planned in the protocol:

1. Although planned in the protocol, the central radiologic review was only incompletely performed due to a variety of reasons (no images submitted from local to central radiologist, when already the first tumor assessment resulted in an overall lesion response of 'progressive disease'; or images were not assessable according to the central radiologist). An incomplete sequence of central assessments cannot be used to derive the primary and secondary efficacy variables. Thus, the trial will be analyzed based on local tumor assessments only.
2. The intention-to-treat (ITT) set will be used for the primary efficacy analysis rather than the per-protocol (PP) set, since this is what is recommended by RECIST criteria (version 1.0, see [Therasse et al. 2000](#): 'All patients included in the study must be assessed for response to treatment, even if there are major protocol treatment deviations or if they are ineligible. [...] All conclusions should be based on all eligible patients.')

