1.1 Populations for analysis

The **safety set** consisted of all patients who received at least one dose of study drug and had at least one post-baseline safety assessment. Patients were analyzed according to treatment received. Of note, the statement that a patient had no adverse events also constituted a safety assessment.

The **intent-to-treat (ITT) set** consisted of all patients who received at least one dose of study drug and had at least one post-baseline assessment of the primary efficacy variable (target/non-target lesion assessment according to RECIST). Patients without any post-baseline assessment of tumor were included if they were defined as progressive disease based on clinical evaluation.

The **per-protocol (PP) set** consisted of all patients of the intent-to-treat population who did not show any major protocol violations. As major protocol violations were considered those that may have an impact on the study outcome. Criteria that were assumed to have such an impact were defined in a Review Meeting before database lock.

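### SAP 1.5.1 bases the objective response rate on central radiologic review, although SAP section 1 restricts the whole analysis to local tumor assessments

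*SAP*

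**What the plan says.** SAP section 1, item 1 of the changes from the protocol, reports that central review was not completed. One reason was that there were "no images submitted from local to central radiologist, when already the first tumor assessment resulted in an overall lesion response of" progressive disease; another was that some images could not be assessed by the central radiologist. It then sets a rule, "An incomplete sequence of central assessments cannot be used to derive the primary and secondary efficacy variables", and concludes: "Thus, the trial will be analyzed based on local tumor assessments only".

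SAP 1.5.1 defines ORR, a secondary variable, as the proportion in whom a complete or partial "response was observed at Visit 6/Week 16 according to RECIST (version 1.0) based on central radiologic review". The same section says "Secondary efficacy variables were analyzed for the ITT set". SAP 1.1 admits to that set treated patients who "had at least one post-baseline assessment of the primary efficacy variable (target/non-target lesion assessment according to RECIST") and also patients classed as progressive on clinical grounds. Neither route requires a central read.

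The other response variables that name a reader use local reads. These are the primary variable (SAP 1.4.1), best overall response including follow-up (SAP 1.4.4) and duration of stable disease, which covers patients "whose best overall response was CR, PR or SD based on local radiologic assessments".

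**The concern.** The two statements cannot both be followed. Section 1 names secondary efficacy variables expressly and allows local assessments only. Section 1.5.1 then takes one secondary variable from the reader that section 1 excludes, without giving a reason or a rule for ITT patients who have no central read. Switching the trial to local reads is disclosed and explained, and is not the problem. The problem is that ORR was left outside the switch.

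What is at stake is whether ORR can be reproduced. An analyst following section 1 would use local reads. An analyst following section 1.5.1 would use an incomplete set of central reads and would have to decide how to treat the gaps. The two could report different figures.

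**Working it through.** **Comparison of the texts**

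| Variable | Place in SAP | Reader named |
|---|---|---|
| All primary and secondary efficacy variables | Section 1, change 1 | Local only |
| Primary variable | 1.4.1 | Local |
| Best overall response including follow-up | 1.4.4 | Local |
| Duration of stable disease | 1.5.1 | Local |
| ORR | 1.5.1 | Central |
| PFS, time to progression | 1.5.1 | None named |

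Both sides of the conflict are current SAP text. Change 1 departs from protocol 7.4, which named the central radiologist. It does not describe an older SAP.

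**Who could be miscounted on the ITT set**

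1. *Images not submitted because the first assessment was progressive disease.* Protocol 5.2 and 6.3.6 take such patients off study at progression. They are not Week 16 responders on the local read, and there is no central read to make them responders. They are non-responders either way.
2. *Images submitted but not assessable centrally.* The local reader may have recorded a response. On a central-read ORR with the ITT denominator, that patient could be counted as a non-responder.

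Of the two stated reasons for missing reads, only the second can lose a local responder.

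**Size per patient**

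The change in ORR for each such patient is 1/n. The n are assumptions: the planned sizes for arms I and II (SAP 1.6), and for arm III the 8 patients enrolled (protocol section 10).

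- Arm I: 1/36 = 2.8 points
- Arm II: 1/24 = 4.2 points
- Arm III: 1/8 = 12.5 points (this arm is descriptive only)

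**Precision around those figures**

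SAP 1.5.1 gives no confidence level for ORR, so I assume the two-sided 80% Clopper-Pearson interval of SAP 1.4.2. With 0 responders the upper limit is 1 − 0.1^(1/n):

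- n = 36: 1 − 0.1^(1/36) = 6.2%
- n = 24: 1 − 0.1^(1/24) = 9.1%
- n = 8: 1 − 0.1^(1/8) = 25.0%

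With 1 responder the intervals are 0.3% to 10.4% for 1/36 and 0.4% to 15.3% for 1/24. One patient counted differently therefore moves the estimate by less than the width of its own interval.

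**The case against.** **The general rule already governs.** Section 1 is explicit, reasoned and trial-wide, so the central-review phrase looks like a leftover that an informed analyst would ignore. That is plausible and limits the importance of the point. It does not remove the conflict, because 1.5.1 is where the variable is defined.

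**ORR is a single Week 16 status, whereas the rule concerns an incomplete sequence.** This fails on the closing sentence of change 1, which restricts the trial to local assessments without qualification.

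**ORR is zero anyway.** The SAP changed the duration analysis "since no patient reached a best overall response of CR or PR". This largely stands as evidence that little is at stake, but it does not settle ORR. Best overall response in SAP 1.4.1 uses local reads at Weeks 8 and 16 and needs two determinations at least 4 weeks apart. Whether an unconfirmed PR first seen at Week 16 counts in ORR is unclear. In the protocol's RECIST supplement, Table Appendix 3 assigns a PR at each single assessment, while the text on best overall response requires a confirming repeat. A reader might infer that such a PR definitely counts; the documents leave it open. If confirmation within those two assessments is required, ORR on local reads is 0% for the patients that statement covers.

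**A large upward bias.** A reader might infer that dropping patients without a central read could double ORR. For example, 2/36 = 5.6% would become 2/18 = 11.1% if half were unread. The documents do not support this: SAP 1.5.1 specifies the ITT set, so dropping those patients is not planned. The unread share and the responder count are also not given anywhere.

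**Conclusion.** The contradiction is certain on the text. As written, ORR would rest on central reads that the SAP itself says cannot be used for secondary variables.

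The consequence is probably small. ORR carries no decision rule and does not touch the primary conclusion, and no best overall response of CR or PR is reported. The supported effect is a possible understatement of 2.8 points (arm I) or 4.2 points (arm II) for each local responder whose images were not assessable centrally. This assumes ITT sizes of 36 and 24 and that patients without a central read are counted as non-responders. The number of such patients is not stated and may be zero.

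Two stronger readings should not be drawn. A reader might infer that responders were lost because their images were never submitted; the only reason given for non-submission is progression at the first assessment, and those patients are not responders. A reader might also infer that the reported ORR was in fact taken from central reads; the documents do not show which reader was used.

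Severity: minor. Confidence is high for the conflict in wording and lower for any numerical effect.

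**What to change.** In the ORR definition in SAP 1.5.1, replace the reference to central review with local radiologic assessments, as in SAP 1.4.1, and keep the ITT denominator. Check which reader was used for the ORR table. If it was the central reader, re-tabulate ORR from the local reads already collected. No extra sentence on protocol 7.4 is needed, because change 1 in SAP section 1 already records that departure.

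The cost is one phrase and, at most, one re-run table, with no new data. The downside is that ORR loses an independent reader, which SAP section 1 already accepts for the trial as a whole.
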